Healthy Design Ltd. Co. is developing the “*Exersides*TM” restraint, a novel, adjustable arm restraint for invasive or non-invasive mechanically ventilated patients.⁶⁻⁸ *Exersides*TM is designed to prevent self-extubation while improving upper arm mobility, and reducing agitation, delirium, and the need for sedating medications. Unlike traditional wrist and mitt restraints, *Exersides*TM permits arm movement but does not allow the hands to reach endotracheal and feeding tubes (Figure 1). This novel restraint provides the least restrictive restraint possible at any time in a patient’s varying ICU course and permits maximum mobility levels commensurate with patient physical and cognitive condition. It is adjustable for patient size and to readily allow varying levels of restraint by bedside nurses. This multi-level restraint will empower nurses to minimize restraint AND sedation simultaneously, rather than relying on sedation to help patients tolerate the restraint. Thus, *Exersides*TM will meet current ‘least restraint necessary’ regulations and ‘best practice’ recommendations.

Preliminary Studies and Data

1. A prototype of the novel *Exersides*TM restraint was designed to prevent self-extubation while minimizing immobility, agitation, and sedation.

Figure 2. Healthy volunteer wearing the *Exersides*TM restraint. Adjustable white straps (lower left) attach to bed and can be titrated to patient needs.

Supported, in part, by a sub-award from R24HD065703, the prototype (shown in Figure 2) was designed to allow complete rotational capacity of the shoulder joint, with comfort flexion at the elbow, while providing a squeezable ergonomic hand grip. The straps that secure the hand at the grip are designed to avoid the anterior wrist to permit use of a radial arterial catheter, when clinically indicated, and render the posterior aspect of the hand accessible for peripheral IVs, if clinically indicated. The device also allows easy access to the arm for blood pressure cuffs and IVs. *Exersides*TM telescopes to adjust to the variable arm length of each patient and has a soft outer shell for cushioning. The wrist straps do not bind circumferentially, as with traditional wrist restraints, to help prevent possible compromise in vascular circulation. Two attachments at the distal arm offer a resistance band tie and a non-flexible tie that can be affixed to a hospital bed, if desired.

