Activity and agitation were qualitatively assessed by analyzing the video recording, demonstrating that patients were active and awake while using *Exersides*TM, with rare agitation observed in the *Exersides*TM group. Sedation medication dosing (propofol in all patients) was measured immediately before and then during the 4-hour period (Table 2). Propofol use, sedation score, time spent moving, and time spent interacting were all generally improved with *Exersides*TM.

Table 1. Healthy volunteer survey (N=6) demonstrating high satisfaction with the *Exersides*TM restraint

	Strongly Agree or Agree	Neutral/Disagree/Strongly disagree
From perspective of simulated PATIENT		
Comfortable	5	1
Safe	6	0
Effective	6	0
Preferable	6	0
More humane	6	0
From perspective of simulated STAFF		
Easy to don/doff	3	3
Easy to change level	5	1
Safe for staff	5	1
Effective	6	0
Preferable	5	1
More humane	6	0

Table 2. Patients using *Exersides*TM restraint vs. traditional wrist restraints required less sedation and spent more time moving, and interacting during 4-hour study period

	Pre-study: Propofol dose (mcg/kg/hour)	During study: Propofol dose (mcg/kg/hour)	During study: SAS*	Time spent moving (hours) during 4-hour period	Time spent interacting (minutes) during 4-hour period
Traditional wrist restraints (n=5)	26±18	20±12	3.2±0.4	0±0	2.2±4.4
Exersides TM restraint (n=5)	28±8	11±10	4±0.7	2.6±1.6	66±74

*Sedation-Agitation Scale; 1=comatose, 4=calm and cooperative, 7=dangerously agitated

Themes derived from qualitative feedback from patients, nurses, and occupational therapists are in Table 3. In the Phase I portion of this STTR, we will revise the device based on existing feedback (Tables 1 and 3) and provide expanded data on safety and feasibility in an independent academic medical center (UVM site).

Table 3: Feedback on prototype from patients, nurses, and occupational therapists

Patients	Nurses	Occupational therapists
Straps pushing upward on hands Happy to be able to move Can scratch nose with arm rod	Better to see patient awake Difficult to adjust hand straps Better for IV placement	Grip too large Shoulder piece effective Easier to hold arm rod than arm More rehab done with awake patient

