3. To conduct a multi-site, within-patient crossover RCT in older mechanically ventilated patients requiring restraint to test the following **hypotheses** regarding *ExersidesTM* vs. traditional wrist restraints:
 - a. *ExersidesTM* allows greater upper extremity **activity**, as measured by actigraphy (primary outcome)
 - b. *ExersidesTM* reduces **delirium, agitation, and use of sedatives**, analgesics and antipsychotics
 - c. *ExersidesTM* has high satisfaction, assessed via both **quantitative and qualitative evaluations**, among ICU clinicians, families and patients.

METHODS AND PROCEDURES

Study Design, Procedures, and Statistical Analysis Plan (all included here for Phase I and then Phase II):

PHASE I (small cohort study to assess feasibility and safety)

Aim 1: To revise the *Exersides™* prototype based on pre-existing user feedback

- For this Aim, we and the company (Healthy Design, Ltd) will utilize the UVM Simulation Center to test the current device in 3 standardized patients. During this session, comfort, safety, and satisfaction will be evaluated in a simulated hospital setting. Following this session, any revision of the novel device needing to occur based on feedback obtained will be performed by the manufacturer before proceeding to Aim 2. Prevention of safety issues listed below in Aim 2 will be addressed during device refinements by surveying for sharp edges or hard protrusions and adding padding, as well as ensuring that securing straps are appropriately positioned, wide and padded.

Aim 2: To demonstrate safety of the *Exersides™* restraint and the feasibility of conducting an RCT (Aim 3, STTR Phase II) by performing a pilot cohort study to assess the restraint in 8 older ICU patients.

- Study Site:** UVM, a large regional hospital with extensive ICU RCT experience, is located close to Healthy Design, with Drs. [name] and [name] having a pre-existing collaborative working relationship.
- Patients (n=8):** We will conduct a study of 8 elderly ventilated ICU patients requiring restraint per an active physician order. See inclusion and exclusion criteria below in Table 4.

Table 4: Inclusion and Exclusion Criteria for Study Entry into STTR Phase I and Phase II Studies

Inclusion Criteria	Exclusion Criteria	Rationale for Exclusion
1. >60 years old	1. Upper extremity impairments that prevent use of novel restraint device (e.g. amputation, arm injury)	Unable to receive proposed intervention

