2. Physician order for use of bilateral wrist restraints	2. Limited mobility of either upper extremity prior to admission (e.g. frozen shoulder, severe arthritis)	Inaccurate data for primary outcome assessment during RCT (i.e. actigraphy)
3. Requiring invasive or non-invasive mechanical ventilation with actual or expected total duration of >48 hours	3. Pre-existing primary systemic neuromuscular disease (e.g. Guillain-Barre)	
4. Expected ICU stay >3 days after enrollment (to permit adequate exposure to proposed intervention)	4. Neuromuscular blocker infusion (eligible once infusion discontinued if other inclusion criteria met)	Unable to perform outcome assessments
5. Not deeply sedated (Richmond Agitation Sedation Scale [RASS] score ≥ -2) ¹	5. Pre-existing severe cognitive impairment or language barrier prohibiting outcome assessment	
	6. Expected death or withdrawal of life-sustaining treatments within 6 days from enrollment	Patients unlikely to complete proposed outcome assessment protocol
	7. Incarcerated	Vulnerable population; ethical issues
	8. Severe skin breakdown on either upper extremity	Unable to receive proposed intervention

- Consent:** As most eligible patients will be unable to make decisions, written informed consent will most often occur via legally authorized representatives (LARs) with participant re-consent upon regaining capacity. See below under section on Consent.

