which time they will be observed by research and nursing personnel, with validated and reliable hourly assessments of sedation/agitation (RASS score). A digital video camera will be set up at the foot of the patient's bed to continuously record his/her movements during the study sessions. Overnight between study Days 1-2 and 2-3, subjects will resume traditional wrist restraints, as per MD order. No sensor or video data will be recorded during overnight periods when study staff are not available. Starting on Day 3 morning, subjects who continue to require restraints (per MD order) will be placed in either traditional or novel restraints device, as per their original randomization (i.e. the device worn for first 4-hr study period on Day 1) for up to 4 more days (i.e. until earliest of restraints no longer needed, death, or ICU discharge). This novel within-patient crossover design allows for increased precision with fewer subjects (see Sample Size) because it controls for confounding effects of patient-specific characteristics via each patient serving as their own control when comparing outcomes (i.e. arm activity) of the novel vs. traditional restraint during Days 1 and 2, along with reduced bias due to randomized allocation of initial study group (novel vs. traditional). Moreover, this design permits more prolonged comparison of novel vs. traditional device (over Days 3 to 6) to measure secondary outcomes (e.g., agitation, delirium, and medication use) that are more accurately evaluated over longer periods of evaluation. The randomization feature of this study design also controls for potential temporal differences in movement (e.g., patient more awake/mobile from 9am-1pm vs. 1pm-5pm). Patient eligibility criteria also help ensure that the study occurs when patients require restraint and are readily assessed for the primary and secondary outcome measures.

- Recurrence of clinical need for restraint and/or ICU readmit:** If a patient ceases to need restraint during the 6-day study period, but then is deemed to need restraint again, the randomly allocated intervention will resume (up to 6-day maximum), with study ending upon ICU discharge (without re-starting if ICU re-admit).

Table 7: Primary & Secondary Outcomes of Efficacy RCT in Aim 3

Outcome		Instrument	Scale	Assessment Timing
Primary Outcome				
1	Upper extremity mobility	Actigraphy (total activity counts per 4 hours)	Continuous	Continuously throughout study
Secondary Outcomes				

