- **Agitation:** Agitation will be measured via RASS (Richmond Agitation Sedation Scale) score¹ assessed by research staff every 60 minutes during the four 4-hour periods (Days 1 and 2) when subjects are using novel and traditional restraints, and then every 4 hours during Days 3-6 when subjects are using their randomly assigned device. RASS is a validated and reliable ordinal measure of sedation/agitation status in the ICU ranging from -5 to +4.¹ All study personnel will be trained in measuring RASS score. We hypothesize that *Exersides™* will reduce **delirium, agitation, and use of sedatives**, analgesics and antipsychotics.
- **Delirium:** Delirium will be measured via CAM-ICU (Confusion Assessment Method for the ICU) at its maximum appropriate frequency of every 4-hours during Days 1-2, and then every 12 hours during Days 3-6. The CAM-ICU score is a validated and reliable binary measure of delirium status in the ICU.¹ All personnel will be trained in measuring CAM-ICU. Our group has extensive experience with CAM-ICU.¹
- **Sedative, analgesic, and antipsychotic medication use:** Throughout the 6-day study period, use and dose of medications will be assessed by chart review. Medications in these categories include, but are not limited to, opiates, benzodiazepines, typical and atypical antipsychotics, propofol, and dexmedetomidine.

Outcome 3: Satisfaction with and acceptability/perceptions of the device

Satisfaction and acceptability will be assessed by the Quebec User Evaluation of Satisfaction with Assistive Technology (QUEST 2.0) survey and by semi-structured interviews. We hypothesize that *Exersides™* will demonstrate high satisfaction, assessed both quantitatively and qualitatively, among ICU clinicians, families and patients.

- **Satisfaction:** The QUEST 2.0 is a valid, reliable, and widely used 12-question survey assessing satisfaction with technological devices.¹ It is scored from 1-5, with >3.26 considered high satisfaction. The QUEST 2.0 has 2 subscales (satisfaction with device and with services). Satisfaction with the *Exersides™* restraint will be assessed using the device subscale, which has good test-retest stability (ICC 0.82).¹⁷

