During the first 2 Days, the primary endpoint (activity) is measured for each period on each day, such that each patient will contribute 4 longitudinal measurements. This primary endpoint is measured as total activity, the sum of the recorded activity counts for the corresponding period/day. Secondary endpoints include agitation (normal vs. sedated/agitated as defined by RASS), delirium (positive vs. negative for delirium based on CAM-ICU, among patients who are not comatose [RASS -4, -5]) and medication use (quantified by computing the total dose of medications received within each class (Outcome 2) using standard equivalency conversions for drugs within each class, as done in our prior research.¹ Analysis will include summary statistics (mean, median, standard deviation and quantiles) of the key co-interventions (see Aim 3I above) and the RCT endpoints (Table 8), separately for each period over the 2 days, stratified by treatment group.

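### The secondary agitation endpoint merges sedated with agitated patients, so its odds ratio cannot show whether agitation fell

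*Combined protocol and SAP*

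**What the plan says.** Hypothesis b of the Phase II Specific Aims is that the novel restraint reduces "delirium, agitation, and use of sedatives", together with analgesics and antipsychotics. Agitation and sedative use are thus separate items. Outcome 2 repeats the hypothesis and describes the instrument: "RASS is a validated and reliable ordinal measure of sedation/agitation status in the ICU ranging from -5 to +4".

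The Statistical Analysis Plan, part a), then turns RASS into two categories: "Secondary endpoints include agitation (normal vs. sedated/agitated as defined by RASS". It does not say which RASS values count as normal. Binary secondary endpoints get a longitudinal logistic model fitted by GEE, with terms for treatment, period and order. Data from Day 3 onward get linear and logistic longitudinal models. No agitated-only or three-category analysis of RASS is specified.

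The protocol expects sedation to change with the device. Background and Significance says nurses will be able to "minimize restraint AND sedation simultaneously, rather than relying on sedation to help patients tolerate the restraint". The title of Table 2 reports that pilot patients on the novel restraint "required less sedation and spent more time moving, and interacting during 4-hour study period". The pilot narrative describes them as awake, "with rare agitation observed in the" novel-restraint group.

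**The concern.** The hypothesis concerns one end of the scale, but the endpoint pools both ends. A favourable odds ratio labelled agitation could come entirely from less sedation. A real rise in agitation could be offset by a fall in sedation. If both fall, the direction is right, but the result still cannot show that agitation fell.

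This bears on how the trial will be read. The primary outcome is total arm movement, and the protocol itself says, under Outcome 1, that recorded movement may be purposeful or may reflect agitation. An agitation-specific estimate would help to interpret a positive primary result, and the merged endpoint cannot supply one. Days 3 to 6 are justified partly as a longer comparison "to measure secondary outcomes (e.g., agitation, delirium, and medication use) that are more accurately evaluated over longer periods of evaluation". If the same coding is used there, the problem carries over.

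**Working it through.** **Whether the sedated category will be populated.** Table 4, inclusion criterion 5, reads "Not deeply sedated (Richmond Agitation Sedation Scale [RASS] score" of -2 or above, so lightly sedated patients can enter. The delirium definition in part a) sets aside RASS -4 and -5, so deeper sedation during the study is foreseen. In the pilot (Table 2, n=5 per group), the mean Sedation-Agitation Scale score was 3.2 with wrist restraint and 4 with the novel device. On that scale 4 is calm, so the difference lies between the sedated side and calm.

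**Formulas.** Let s be the proportion sedated and a the proportion agitated, with subscript 1 for wrist restraint and 2 for the novel device, and odds(p) = p/(1-p).

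- Planned (merged) OR = odds(s2 + a2) / odds(s1 + a1)
- Agitation OR = odds(a2) / odds(a1)

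The merged OR contains s and a only through their sum. That follows from the definition and needs no assumed rate.

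**Inputs.** The plan states no rate or odds ratio for agitation, so there is no figure to reproduce. All rates below are assumed: a1 = 10% and s1 = 10, 20, 30 or 50%.

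| Case | Merged OR at s1 = 10 / 20 / 30 / 50% | Agitation OR |
|---|---|---|
| A: sedation falls by one third, agitation unchanged | 0.80 / 0.71 / 0.64 / 0.51 | 1.00 |
| A, with a one-fifth fall in sedation | 0.88 / 0.82 / 0.77 / 0.67 | 1.00 |
| B: agitation halves, sedation unchanged | 0.71 / 0.78 / 0.81 / 0.81 | 0.47 |
| C: sedation falls by one third, agitation halves | 0.53 / 0.52 / 0.50 / 0.41 | 0.47 |
| D: sedation falls by one third, agitation doubles (adverse bound, not predicted by the documents) | 1.45 / 1.17 / 1.00 / 0.76 | 2.25 |

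Example, case A at s1 = 30%: s1 + a1 = 0.40 and s2 + a2 = 0.20 + 0.10 = 0.30. The merged OR is (0.30/0.70)/(0.40/0.60) = 0.64.

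**Same merged result, different agitation.** At s1 = 30% and a1 = 10%, case C gives 20% + 5% = 25%. Halving sedation with agitation unchanged gives 15% + 10% = 25%. Both yield (0.25/0.75)/(0.40/0.60) = 0.50, but the agitation ORs are 0.47 and 1.00.

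**Sensitivity to the assumed rates.**

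- With a1 = 5%, case A gives 0.75 / 0.67 / 0.62 / 0.51.
- With a1 = 20%, case A gives 0.85 / 0.75 / 0.67 / 0.49. Case D gives 2.04 / 1.71 / 1.50 / 1.18 against a true 2.67, so the rise is diluted but not reversed.
- With a1 = 10% and only 5% sedated, case A shrinks to 0.87.

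**An ordinal model as an alternative.** A proportional-odds fit to the three categories (sedated, normal, agitated) with one common OR for higher RASS gives, for case C with a1 = 10%, 0.89 / 1.11 / 1.28 / 1.61. Both components improve, yet three of the four settings point towards more agitation. A single-parameter ordinal model therefore also mixes the two.

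**The case against.** The strongest reply is that the plan has other information on agitation. Table 7 lists video recording, on a continuous scale, beside RASS, and part a) applies its linear models to continuous secondary endpoints. Sedative, analgesic and antipsychotic dose is a separate endpoint, so a merged result driven by less sedation would often come with a visible fall in dose. Part a) also plans means and quantiles of the endpoints by period and treatment group (it cites Table 8, but the endpoints are in Table 7). If applied to the raw score, these would show which side moved. These points lower the risk of misreading, but none isolates agitation: no video variable is defined or given a named model, dose is not agitation, and summary statistics give no modelled device effect.

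A second reply is that being at the calm, awake target is a coherent outcome and fits the sites' stated aim of wakefulness. That is true, but the plan labels the endpoint, and states the hypothesis, as agitation.

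Three limits stand. The coding for Days 3 to 6 is inferred, since the plan mentions only an agitation assessment and logistic models there. Full masking of a rise in agitation depends on agitation being uncommon. The endpoint is secondary and declared hypothesis-generating, without multiplicity correction.

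**Conclusion.** The concern holds. As written, the agitation endpoint does not answer the plan's own hypothesis, because its odds ratio cannot separate less agitation from less sedation. That conclusion needs no assumed rate. The size does: with 10% agitated and 10% to 50% sedated under wrist restraint, a one-third fall in sedation alone produces an apparent agitation OR of 0.80 to 0.51. The artefact remains at 5% and 20% agitated and shrinks as the sedated share falls. The missing cut-off for normal is a separate gap in the same definition.

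This should be fixed, but its reach is limited. Raw RASS is collected, so nothing is lost, and the primary analysis and sample size are untouched.

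**What to change.** In the Statistical Analysis Plan, part a), replace the merged endpoint with two binary endpoints: agitated (RASS above 0, yes/no) and sedated (RASS below a stated cut-off, yes/no). The plan gives no cut-offs, so the investigators should confirm both in the text. Fit each endpoint with the planned logistic GEE for Days 1 and 2 and with the planned logistic models for Days 3 to 6, and state that the same coding applies in both windows. A three-category nominal model with separate device effects for sedated and agitated would also serve; a single proportional-odds parameter would not. If the investigators also want a measure of being at the calm target, the merged variable can be kept under that name. State that the planned summary statistics will be applied to the raw RASS score by device, and correct the table reference.

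The cost is SAP wording only. It adds one hypothesis-generating comparison and lowers precision for agitation. With one value per period, 54 x 4 = 216 values would include about 22 agitated at 10% (216 x 0.10 = 21.6) or about 11 at 5% (216 x 0.05 = 10.8). With so few events the unstructured working correlation may not fit stably, so a simpler fallback structure should be named in advance.

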- **Study Sites:** We will recruit patients from 3 hospitals: UVM, JHU and UCLA. These sites were selected due to successful prior collaborations, experience in ICU RCT recruitment, similar sedation practice (Prelim Data 6), experience in ICU mobility/actigraphy, and similar “usual care” (Prelim Data 6). A study overview is in Figure 3.

- **Data Coordinating:** Data coordination will occur through integrated efforts between Healthy Design and all 3 study sites, with full support for design, conduct, monitoring, and analysis. An employed data coordinator will create a study database in RedCAP

and will manage data from all 3 enrolling sites. Data coordination, cleaning, and subsequent analyses will be overseen by Drs. [name] (PhD biostatistics faculty/ co-I) with Drs. [name], [name], and [name]. [name] will oversee RCT conduct, including regulatory/ NIH reports. And employed study monitor will conduct site monitoring visits during the RCT.

- **Study Leadership of RCT:** To address leadership and communication issues, an Executive Committee (“EC”: Drs. [name], [name], and [name], along with [name] [Project Manager, UVM]) will meet twice monthly by phone to discuss RCT conduct. For issues that require broader input, the RCT also will have a Steering Committee that includes the EC plus Drs. [name] (UCLA site PI), [name] (Biostatistician), [name] (Nurse co-investigator), [name] (aging/delirium co-investigator) that will meet monthly or as needed. Each site-PI will supervise daily operations, along with site research staff supported by per-patient capitation payments. All investigators will co-author publications, with author order mutually agreed upon in advance.
- **Patients (n=54):** Eligibility criteria are identical to the cohort study in Aim 2 (Table 5).
- **Consent:** As in the study in Aim 2 (STTR Phase I), consent will most often occur via LARs with participant re-consent upon regaining capacity. See below under section on Consent.
- **Randomization:** After consent, patients will be randomized (1:1) to Group A vs B (Fig. 4) via UVM’s web-based system (24 hrs/day), with variable-sized blocks of 2 or 4, stratified by site.

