- **Sample size:** Sample size was determined for the primary outcome, arm activity, as assessed by actigraphy over Days 1 and 2 (defined as total activity counts per 4-hour period: 9am-1pm and 1pm-5pm). Although Phase II is 24 months long, there are only 18 months for recruitment, as we need 3 months for startup and 3 months for close out (Table 10). Across the 3 study sites, we expect to recruit 1 patient per site per month during the 18-months, yielding a total N=54. Experience enrolling ICU patients in RCTs at each site.¹ suggests that 1 patient/month/site is feasible and mirrors empirical data, with our analysis of 33,106 patients from 23 RCTs, demonstrating median (IQR) enrollment of 0.90 (0.50–1.79) patients/month per site.²⁰

Assuming N=54, we calculated the treatment effect (i.e. the relative change in the median total activity) that can be detected with 80% power and 5% Type I error rate. We used the following assumptions (these data were informed by our preliminary data with modest adjustments for expected differences for the proposed 3-center study): (1) 9am-1pm median total activity = 3000, (2) 1pm-5pm median total activity = 2700, (3) variance of Log(total activity) set conservatively to 2.5 and 6.0 for 9am-1pm and 1pm-5pm periods, respectively, (4) Log(total activity) has 0.85 correlation within a patient over time, and (5) no cross-over effect of the restraints. Using N=10,000 simulation, the 54-patient sample size can

detect a 56% relative increase in median total activity comparing the novel vs. traditional restraint (median of 3000 vs. 4674).

- **Statistical Analysis Plan**

a) Summary for all Aims: All analyses **will follow the intention-to-treat (ITT) principle**. A 2-tailed p-value <0.05 will be statistically significant. As described in the Study Design (Section 3K), the within-patient crossover design removes patient-specific effects from evaluation of the treatment effect. Potential pitfalls of this design include order effects, carryover effects, and patient dropout. To avoid order effects, we randomize whether patients start the trial with the novel vs. traditional restraint (Figure 4). Carryover effects (i.e. one part of the study affecting subsequent parts) and drop out considerations are discussed further below.

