To estimate the effect of the novel restraint, a linear model will be fit for the Log(total activity) as a function of main terms for treatment (Group A vs. B), time period (1pm-5pm vs. 9am-1pm), and treatment order (BA/AB vs. AB/BA). The natural logarithm is applied to the primary endpoint to reduce right skew in the distribution of total activity, with the exponentiated regression coefficient for the main term for treatment (A vs. B) in the linear regression model representing the relative difference in median total activity comparing the novel vs. traditional restraint, which will quantify the treatment effect. The linear model will be fit using weighted least squares to account for the correlation in the primary endpoint within a patient over time; the correlation structure will be specified as unstructured and allow for the possibility that the variance of the primary endpoint may be different in each period/day. The same linear models will be applied to the continuous secondary endpoints (e.g. medication dose). For the binary secondary endpoints, the effect of the novel vs. traditional restraint will be quantified using a longitudinal logistic regression model as a function of the same covariates (treatment, period, and treatment order). The longitudinal logistic regression model will be fit using generalized estimating equations allowing for an unstructured within-patient correlation structure. Activity, agitation, delirium and medication use will continue to be measured up to ICU discharge, death or Day 6. Starting on Day 3, the endpoints will be expressed as every 4-hour total activity counts, agitation assessment and total medication use, as well as every 12-hour delirium. With the data starting on Day 3, we will explore the long-term effects of the restraints by fitting linear and logistic longitudinal regression models that include main terms for treatment and time and the interaction of treatment and time. Time will be modeled as a restricted cubic spline with degrees of freedom selected by model fit statistics. As secondary outcomes are hypothesis-generating, we will not correct for multiple comparisons, but will consider the number of comparisons when interpreting results.

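### The Days 1-2 primary model has no Day 1 versus Day 2 term; adding one is a cheap gain in precision and robustness, not a correction of a threatened result

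*Combined protocol and SAP*

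**What the plan says.** Under Statistical Analysis Plan, part a), activity on the first two days is totalled for each period of each day, "such that each patient will contribute 4 longitudinal measurements". The linear model for log activity has three main terms: treatment, "time period (1pm-5pm vs. 9am-1pm), and treatment order (BA/AB vs. AB/BA). Period therefore has two levels, morning and afternoon, and order is the two-day sequence. The within-patient covariance is unstructured, with a variance that may differ by period and day. Continuous secondary endpoints use the same linear model. Binary ones use a longitudinal logistic model with the same covariates.

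Day appears nowhere in the mean model. Descriptive summaries are planned by period over the two days, a sensitivity analysis adds time-varying factors such as organ failure, and a time term enters only the models that start on Day 3.

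**The concern.** Four windows are modelled with two period means, so a change in activity from Day 1 to Day 2 has no place in the mean. The other features do not supply one: the unstructured covariance frees variances and correlations, not means, and the order term is constant within a patient. The plan itself anticipates change over time. The Study design paragraph cites changing condition in critically ill patients as a reason for the crossover, and the SAP concedes that the crossover does not fully control time-varying factors.

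Two things are at stake. An unmodelled day shift is read as residual variation, which widens the interval for the device ratio. And if Day 2 data are lost unevenly by sequence or by device, part of the shift can enter the device contrast. Day 2 sessions can be lost, because the device is used only while a restraint order is active (Risks/Benefits).

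**Working it through.** **Inputs from the documents.** "yielding a total N=54"; "patients will be randomized (1:1) to Group A vs B", hence 27 per sequence; "variance of Log(total activity) set conservatively to 2.5 and 6.0 for 9am-1pm and 1pm-5pm periods, respectively"; within-patient correlation 0.85 (Sample size); four windows per patient; device order reversed on Day 2 (Risks/Benefits); "A 2-tailed p-value <0.05 will be statistically significant"; "with 80% power and 5% Type I error rate". I read the treatment term as novel versus traditional device in each window.

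**Assumption.** The documents give no day effect. Day 2/Day 1 activity ratios of 1.25 to 3 are used, with d the log of the ratio.

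**The plan's own figure.** The plan says that it can "detect a 56% relative increase in median total activity comparing the novel vs. traditional restraint (median of 3000 vs. 4674), a log ratio of ln(4674/3000) = 0.443. With the standard error of 0.0990 derived below, the detectable log ratio at 80% power is (1.960 + 0.842) × 0.0990 = 0.277, a 32% increase. An unweighted fit (SE 0.109) gives 36%. The stated 56% was therefore not reproduced at N=54. The simulation settings are not given, so the reason cannot be settled, and it does not affect this point. Here 0.443 serves only as a yardstick.

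**Complete data: bias.** Write AM1, PM1, AM2, PM2 for the four windows. In the sequence that starts with the novel device, the device contrast is a(AM1 - AM2) - (1 - a)(PM1 - PM2), with a the weight on the morning comparison. A common day shift contributes -(2a - 1)d. In the other sequence the sign reverses and the contribution is +(2a - 1)d. With 27 complete patients in each, the two cancel and the bias is 0.

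**Complete data: standard error.**
- Var(AM1 - AM2) = 2 × 2.5 × 0.15 = 0.75. Var(PM1 - PM2) = 2 × 6.0 × 0.15 = 1.8. With a common correlation these two differences are uncorrelated.
- With a Day term, minimise 0.75a² + 1.8(1 - a)². This gives a = 1.8/2.55 = 0.71, a minimum of 0.529, and SE = √(0.529/54) = 0.0990.
- Without a Day term, the shift enters the fitted covariance, so the quantity minimised is 0.75a² + 1.8(1 - a)² + (2a - 1)²d², with solution a = (3.6 + 4d²)/(5.1 + 8d²).

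| Day 2/Day 1 ratio | a | Minimum | SE without Day | Increase over 0.0990 |
|---|---|---|---|---|
| 1.5 | 0.664 | 0.552 | 0.1011 | 2% |
| 2 | 0.617 | 0.576 | 0.1033 | 4% |
| 3 | 0.571 | 0.600 | 0.1054 | 6% |

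As d grows without bound, a tends to 0.5 and the SE to √(0.6375/54) = 0.109.

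Simulated power at a true ratio of 1.32, with versus without Day, was 81.1% versus 79.5% (×1.5) and 81.5% versus 78.7% (×2).

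**Uneven Day 2 losses.** The planned fit, with the unstructured covariance estimated from its own residuals, was solved to convergence on expected moments. Activity is assumed to double on Day 2. SE is the model-based value without a Day term.

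| Loss | Shift in log ratio | SE | Shift/SE |
|---|---|---|---|
| Whole Day 2, 3 vs 2 patients by sequence | 0.002 | 0.106 | 0.02 |
| Whole Day 2, 5 vs 0 | 0.009 | 0.106 | 0.09 |
| Whole Day 2, 8 vs 2 | 0.014 | 0.109 | 0.12 |
| Day 2 novel session only, 5 patients (3 and 2) | -0.013 | 0.105 | 0.13 |
| Day 2 novel session only, 10 patients (5 and 5) | -0.031 | 0.107 | 0.29 |

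For whole-day losses the first count is the sequence that starts with the novel device. If the heavier loss is in the other sequence, the sign reverses. With a Day main effect the shift is 0 in every row.

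**The case against.** The strongest reply is that the design already does most of the work. Device is balanced against day within every patient, so a common day shift cannot bias complete data, and an unweighted fit is unbiased under any imbalance in whole-day losses. That stands.

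The planned fit also partly corrects itself: a larger shift pushes the morning and afternoon weights towards equality. For whole-day loss in 5 versus 0, the shift falls from 0.009 when activity doubles to 0.006 when it triples. A reader who fixes the covariance at the assumed variances and correlation would find 0.021 for 5 versus 0 and 0.028 for 8 versus 2. The plan does not fix the covariance; it estimates it, and under that fit those figures are more than halved.

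The scenarios are also unfavourable relative to the plan's expectations. Minimizing missing data anticipates at most 5-10% missing, unrelated to allocation, and allows enrolment up to 60. Five of 54 is 9%, with every loss in one sequence; ten of 54 is 19%, above the stated range. This limits how much weight the bias can bear. It does not show that the Day term is superfluous. Session losses tied to the novel device produce a shift even when the sequences lose similar numbers, and the precision cost arises with no losses at all. The descriptive summaries and the sensitivity analysis may reveal day-to-day change, but neither puts Day in the primary model.

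**Conclusion.** The omission is real, and no other part of the plan fills it. Its consequences are small: no bias with complete data; a standard error 2% to 6% larger if Day 2 activity is 1.5 to 3 times that of Day 1; and, with uneven losses and a doubling, a shift of about 0.1 to 0.3 standard errors, against a log target of 0.443.

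A reader might infer that the missing term biases the primary device ratio in general, or puts the trial's conclusion in doubt. The documents do not support that: both devices are worn on each day in reversed order, and simulations showed no clear difference in type I error between the models with and without Day.

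The sizes rest on the printed variances and correlation, on assumed day ratios, and on assumed patterns of loss. No size was calculated for the secondary endpoints. Losses that depend on a patient's own activity are a separate problem, which a Day term may not fix.

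**What to change.** In Statistical Analysis Plan, part a), add a Day main effect (Day 2 versus Day 1) to the primary model, next to treatment, period and treatment order. Make the same change in the Days 1-2 models for medication dose, agitation and delirium, which reuse these covariates. A Day-by-period term, which would give each of the four windows its own mean, is optional; no calculation here shows a need for it.

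The cost is one phrase in the SAP and one degree of freedom (two with the optional term), with no new data and no change to the design. Make the change before outcome data are seen by treatment, so that the term cannot look data-driven.
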